8.2. Procedure for reporting

All adverse event reporting will be in accordance with the UH Bristol 'Research Safety Reporting Policy' (http://www.uhbristol.nhs.uk/media/2518477/research_safety_reporting_sop_009_uhbristol_r_i_v8.0_19.10.1 5.pdf. A formal SOP and flowchart will be developed to describe the reporting procedure in detail.

All Adverse Events

All AEs will be reported by the Chief Investigator from the time a signed and dated informed consent form is obtained until completion of the patient follow-up at 28 days after randomisation. Adverse events described in the Patient Information Sheet, Protocol or in the pharmacological documentation associated with the trial drug will be monitored and recorded as non-reportable. This includes the potential incidence of tympanic membrane perforation, which may occur in up to 7% of children with AOM. The trial training and recruitment processes will be carefully designed to ensure that clinicians and parents will be vigilant to this potential problem, and parents will receive training to immediately recognise the signs that tympanic membrane perforation may have occurred (discharge from the ear, and/or sudden relief of the child's ear pain), and know what to do (stop treatment with ear drops).

If a Responsible Clinician or other member of the research team becomes aware that a trial-related SAE has occurred beyond the 28 day period this will also be reported to the Sponsor. Those occurrences meeting the definition of SAEs must be reported using the Serious Adverse Event Form, including any related SAE which a Responsible Clinician believes has occurred beyond the trial follow-up period). UH Bristol, on behalf of the Sponsor, will evaluate any safety information that is spontaneously reported by a CI.

All AEs, regardless of seriousness, severity, or presumed relationship to trial drug, must be recorded in the source document and the CRF, together with any measures taken. All Centre PIs must record in the CRF their opinion concerning the relationship of the adverse event to trial therapy. UH Bristol, on behalf of the Sponsor, assumes responsibility for overseeing the appropriate reporting of serious adverse events to the regulatory authorities, in line with the SLA.
All emerging pharmacovigilance data which may be related to activities carried out by the IMP and placebo supplier will be notified to the supplier.

Serious Adverse Events (SAEs)

All SAEs must be reported to the UH Bristol contact ([contact] or [contact]) and Centre PI by a delegated member of the research team within 24 hours of their knowledge of the event. The Chief Investigator and Sponsor should also be informed.

All SAEs that have not resolved by the end of the trial (i.e. by the end of the 28 days of the post-randomisation follow-up period), or that have been not resolved upon discontinuation of the participant's participation in the trial, must be followed until any of the following occurs:

- the event resolves
- the event stabilises
- the event returns to baseline, if a baseline value is available
- the event can be attributed to agents other than the trial drug or to factors unrelated to trial conduct
- when it becomes unlikely that any additional information can be obtained (participant or health care
 practitioner refusal to provide additional information, lost to follow-up after demonstration of due
 diligence with follow-up efforts)

The death of a participant is considered an SAE, as is any event requiring hospitalisation (or prolongation of hospitalisation) that occurs during the course of a participant's participation. Exceptions to this are hospitalisations for:

- social reasons in absence of an adverse event
- in-clinic protocol measures
- surgery or procedure planned before entry into the trial (must be documented in the CRF)

Suspected Unexpected Serious Adverse Reaction (SUSAR)

All relevant information about a SUSAR which occurs during the course of the trial and is fatal or life-threatening will be reported within 7 days to the MHRA by UH Bristol, on behalf of the Sponsor. The expectedness of an adverse event will be determined by whether or not it is listed in the Summary of Product Characteristics, the British National Formulary and study protocol. UH Bristol will work with the research team to support the reporting process for the NHS REC.

All relevant information about a non-fatal or life-threatening SUSAR which occurs during the course of the study will be reported within 15 days to the MHRA and the relevant ethics committee by UH Bristol, on behalf of the Sponsor. The expectedness of an adverse event will be determined by whether or not it is listed in the Summary of Product Characteristics, the British National Formulary and study protocol.

8.3. 'Expected' Adverse Events and Reactions

Any symptom, side effect or adverse event listed in the Summary of Product Characteristics will not be regarded as unexpected. However, since no known common side effects are listed in the Auralgan SmPC equivalent any adverse event deemed related to the IMP will be regarded as unexpected.

8.4. Treatment Stopping Rules

The trial may be prematurely discontinued by the Sponsor, Chief Investigator, Regulatory Authority or Funder on the basis of new safety information or for other reasons given by the Data Monitoring Committee / Trial Steering Committee regulatory authority or ethics committee concerned.

The trial may also be prematurely discontinued due to lack of recruitment or upon advice from the Trial Steering Committee, who will advise on whether to continue or discontinue the trial and make a recommendation to the Sponsor. If the trial is prematurely discontinued, active participants will be informed and no further participant data will be collected.

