8.1. Definitions

Adverse Event (AE)

AEs are defined as any untoward medical occurrence in a clinical trial participant. An AE does not necessarily have to have a causal relationship with the trial treatment. An AE can therefore be any unfavourable and unintended sign (including an abnormal finding), symptom or disease temporally associated with the use of a medicinal (investigational) product, whether or not related to the medicinal (investigational) product. (International Conference on Harmonisation [ICH] definition). This includes any occurrence that is new in onset or aggravated in severity or frequency from the baseline condition, or abnormal results of diagnostic procedures, including laboratory test abnormalities.

All AEs will be recorded in the Case Report Form (CRF) for the duration of the child's direct involvement in the trial. This is 8 days, i.e. the day of randomisation (Day 1) plus the 7 succeeding days. For the 10% of children whose ear pain may be unresolved by day 7, AEs will be recorded until illness resolution, which is defined as the point at which the parent-reported ear pain score for the child has been zero for two consecutive days without medication.

Serious Adverse Event (SAE)

A SAE is defined by ICH as any untoward medical occurrence that at any dose of the trial medication meets any of the following conditions:

1. Results in the death of the participant

2. Is life-threatening

The term "life-threatening" refers to an event in which the participant was at risk of death at the time of the event; it does not refer to an event which hypothetically might have caused death if it were more severe.

3. Requires in-patient hospitalisation or prolongation of existing hospitalisation

For any event that may not be immediately life-threatening or result in death or hospitalisation, but may jeopardise the participant or may require intervention to prevent one of these outcomes, the CI should exercise his/her scientific and medical judgement to decide whether or not such an event requires expedited reporting to UH Bristol (who acts on behalf of the Sponsor in these instances).

4. Results in persistent or significant disability / incapacity

Any event that seriously disrupts the ability of the participant to lead a normal life, in other words leads to a persistent or permanent significant change, deterioration, injury or perturbation of the participant's body functions or structure, physical activity and/or quality of life.

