CEDAR eligibility criteria have been designed to minimise the risk of participant harm and 'Responsible Clinicians' will be reminded they retain responsibility for assessing eligibility. There are two eligibility issues to be closely monitored. First, Responsible Clinicians must be satisfied that a 'no' or 'delayed' antibiotic prescribing strategy is safe. Second, there is a theoretical risk of ototoxicity if the drops are used in the presence of a tympanic membrane perforation. Since 7% of children with AOM may experience a tympanic membrane perforation, the trial training and recruitment processes will ensure that Responsible Clinicians will be reminded to be vigilant to this potential problem, and parents will receive training to immediately recognise the signs that this has occurred (discharge from the ear), in which case further treatment with ear drops will stop. Furthermore, we will ask parents to record, in the daily Symptom and Recovery Questionnaire, whether there is any discharge from the child's ear and remind them to continue to be vigilant regarding this potential adverse event. In February 2014 we searched the MHRA and FDA web sites and neither these sites nor trials¹ of similar drops have reported this adverse event. Moreover, we will also monitor children's medical records for reports of deafness, and conduct the OMQ-14 quality of life questionnaire at 3 months, which includes questions regarding parental perception of their child's hearing.

Adverse (including serious) events will be collected directly both from parents (Symptom and Recovery Questionnaire) and at the primary care notes review. Parents will be asked to record all new symptoms (although we recognise that this may involve recording some 'normal symptoms of daily life' [Tan et al 2014] and these data will be closely monitored by the Trial Research Nurse during the follow-up telephone calls.

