APPENDIX 10: Participant Withdrawal

Parents have the right to withdraw their children, and children have a right to withdraw themselves, from the trial at any time for any reason, without their medical care being affected. Parents and children also have the right to decline to continue with any aspect of the research, without withdrawing and without their medical care being affected.

Data already collected will continue to be used in the trial and parents who withdraw their children from the trial will be asked if they are still willing to provide follow-up data via the Symptom and Recovery Questionnaire. Furthermore, we intend to conduct telephone interviews with parents who decide to withdraw (n=10). If a child is withdrawn, the reason for and type of withdrawal will be documented in the CRF. For example, type of withdrawal may include:

- 1. Trial use of baseline (CRF) data
- 2. Use of trial medication
- 3. Completing Symptom and Recovery Questionnaire
- 4. Receiving telephone calls, letters, email or texts to support Symptom and Recovery Questionnaire completion
- 5. Review of their primary care record
- 6. Completion of the postal Quality of Life (QoL) questionnaire at 3 months
- 7. Any combination or all of the above

The Principal Investigators also have the right to withdraw children from the trial drug in the event of inter-current illness, Adverse Events (AEs), Serious Adverse Events (SAEs), Suspected Unexpected Serious Adverse Reactions (SUSARs), protocol violations, administrative reasons or other reasons. The reason for withdrawal will be documented in the CRF. If the child is withdrawn due to an adverse event, the investigator will arrange for follow-up visits or telephone calls until the adverse event has resolved or stabilised. It is understood by all concerned that an excessive rate of withdrawals can render the trial un-interpretable, therefore unnecessary withdrawal of children will be avoided.

We will request return of the trial Medicine Packs from the parents of children who are withdrawn from the trial. Recruitment will continue until the required number of follow-up datasets are received, thereby replacing any children who have been withdrawn before Symptom and Recovery Questionnaire outcomes are collected.

A formal SOP will be developed to describe the process for declining to continue with elements of the research and for withdrawing from the trial.

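### Section 8.4 bars all data collection after any early stop, safety stops included, which contradicts the SAE follow-up rule in section 8.2 and makes no exception for planned safety follow-up

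*Protocol*

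**What the plan says.** Section 8.4 (Treatment Stopping Rules) lets the sponsor, chief investigator, regulator or funder discontinue the trial "on the basis of new safety information or for other reasons given by the Data Monitoring Committee" and other bodies. It adds poor recruitment and steering committee advice as further grounds. It then sets one consequence for every ground: "If the trial is prematurely discontinued, active participants will be informed and no further participant data will be collected". The section draws no distinction by reason for stopping and refers to no other follow-up rule.

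Other parts of the protocol bear on the same children:

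- **Section 8.1** sets the period for recording adverse events in the case report form: "This is 8 days, i.e. the day of randomisation (Day 1) plus the 7 succeeding days". It is longer where ear pain has not resolved.
- **Section 8.2** has adverse events reported "until completion of the patient follow-up at 28 days after randomisation". For serious events it covers "All SAEs that have not resolved by the end of the trial", and also those "or that have been not resolved upon discontinuation of the participant's participation in the trial, must be followed until any of the following occurs"; the list that follows includes resolution and stabilisation. It also requires a trial-related SAE that comes to the team's notice after 28 days to be reported to the sponsor.
- **Section 10.2** includes SAEs in the Month 3 primary care notes review.
- **Section 16** deals with the theoretical risk of ototoxicity after perforation. It says that "we will also monitor children's medical records for reports of deafness" and that the OMQ-14, which has hearing questions, is completed at 3 months.
- **Appendix 10** says that for a child withdrawn because of an adverse event, "the investigator will arrange for follow-up visits or telephone calls until the adverse event has resolved or stabilised".

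**The concern.** The order to stop collecting data is absolute, and it applies to a safety stop as much as to a stop for poor recruitment. After a safety stop, the children already given drops are the people in whom the signal has to be characterised. Staff who followed section 8.4 to the letter would end the remaining diary days and calls, the rest of the 28-day window, and the 3-month search of records and hearing items. Staff who followed section 8.2 would keep collecting data on open SAEs. The protocol does not say which section prevails, and data not collected at that time cannot be recovered later.

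The contrast with Appendix 10 is awkward. Withdrawing one child because of an adverse event preserves follow-up of that event, and parents who withdraw a child are asked whether they will still provide follow-up data. Stopping the whole trial for safety carries no such provision.

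**Working it through.** **1. Section 8.4 against the other rules.** The protocol states no figure on this point, so the main check is textual.

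| Safety data | Where planned | Position after an early stop |
|---|---|---|
| SAE already open at the stop | 8.2: must be followed | Direct contradiction: 8.4 forbids collecting data, 8.2 requires it |
| Non-serious adverse event, open or new | 8.1: recorded to Day 8; 8.2: reported to Day 28 | Ended by 8.4; the 8.2 follow-up duty covers SAEs only |
| SAE that begins after the stop | 8.2 (28-day window); 10.2 (Month 3 notes review) | Active collection ended by 8.4; 8.2 still has a trial-related SAE reported if someone becomes aware of it after 28 days |
| Deafness or hearing problems | 16 and 10.2: records and OMQ-14 at 3 months | Active search ended by 8.4 |
| Event that led to an individual withdrawal | Appendix 10: followed until resolved or stabilised | Appendix 10 does not address trial closure, so it neither contradicts 8.4 nor fills the gap |

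The one direct contradiction is with section 8.2, for open SAEs. The other rows are planned safety data for which section 8.4 makes no exception.

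**2. Scale, for illustration only.** Inputs:

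- 501 randomised children in 24 months (section 6.8).
- Equal allocation of 10:10:10 (section 12.3), so two thirds receive drops and one third receive active drops.
- Assumptions made here: even recruitment, a stop at a random date once the three-arm phase is under way, 30.44 days per month, and 3 months taken as 91 days.

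Formula: children inside a window at the stop = monthly rate × window in days / 30.44.

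Monthly rate: 501 / 24 = 20.9.

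| Window | Calculation | All arms | Any drops (2/3) | Active drops (1/3) |
|---|---|---|---|---|
| Days 1–8 | 20.9 × 8 / 30.44 | 5.5 | 3.7 | 1.8 |
| 28 days | 20.9 × 28 / 30.44 | 19.2 | 12.8 | 6.4 |
| 3 months | 20.9 × 91 / 30.44 | 62.4 | 41.6 | 20.8 |

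The windows are nested. Of the 62 or so children awaiting the 3-month review, about 62.4 − 5.5 = 57 would already have passed Day 8. The possible loss of the primary outcome is therefore about 5.5 / 501 = 1.1% of the planned sample.

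Sensitivity to the recruitment period: if the 501 children took 18 months, about 55 children on drops would be awaiting the 3-month review; if they took 30 months, about 33.

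**The case against.** The best defence is that section 8.4 is a general closing sentence and section 8.2 a specific duty, so the specific rule can be read as qualifying the general one. On that reading a child with a known, open SAE keeps follow-up. This stands as far as it goes, and it rules out three stronger readings that a reader might infer.

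- **That a safety stop would end all follow-up of exposed children.** The documents do not support this, because section 8.2 retains an explicit duty for unresolved SAEs.
- **That late harm would go undetected.** Section 8.2 still has a trial-related SAE reported if someone becomes aware of it after 28 days. What is lost is the active search at 3 months. Methaemoglobinaemia is a poor example of late harm: the product information in Appendix 8 says its signs may appear within minutes to hours, and a case grave enough to stop the trial would very probably be an SAE covered by section 8.2. Hearing loss is the better example, and section 16 calls that risk theoretical.
- **That about 12.5% of the sample would be lost (62.4 / 501).** Most of those children would already have their Day 8 outcome, and the figure rests on an assumed even rate. Section 6.5 gives quarterly presentation probabilities from 0.062 to 0.153, about a 2.5-fold swing. The synopsis has recruitment continue until the sample size is reached. A stop for poor recruitment would itself imply a lower rate.

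It is also fair to say that section 16 and Appendix 10 do not address trial closure. A closure rule that cuts planned procedures short does not strictly contradict them.

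The defence does not close the gap. The duty in section 8.2 does not reach non-serious events, it does not provide for active collection of events that begin after the stop, and it does not preserve the 3-month hearing check. Nothing in section 8.4 tells staff that section 8.2 overrides it.

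**Conclusion.** The point holds as an internal contradiction with a gap beside it. Section 8.4 conflicts directly with section 8.2 on open SAEs. It makes no exception for the other safety data planned in sections 8.1, 8.2, 10.2 and 16, and it sits badly with Appendix 10. This is a rule the protocol states, so it is not a matter of detail left to an analysis plan.

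The sentence takes effect only if the trial is stopped early. If the trial completes, the analysis, the power and the primary estimate are unaffected. If it stops, the cost falls on safety information far more than on efficacy: under the even-recruitment assumption, about 42 children on drops, about 21 of them on active drops, would lose the planned 3-month check, while 5 to 6 children across all arms would lose the Day 8 outcome. These counts show scale only; the contradiction does not depend on them.

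**What to change.** Replace the last sentence of section 8.4 and cross-refer to section 8.2. Suggested text:

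> If the trial is stopped early, recruitment will end and parents of children in follow-up will be told. With continuing consent, the safety follow-up already planned for randomised children will be completed: adverse event recording and the Day 8 call, the 28-day reporting window, SAE follow-up under section 8.2, and the 3-month notes review and hearing items.

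This concerns data collection only and leaves the grounds for stopping and the use of the drops as they are. If the sponsor wants some non-safety items to lapse after a stop for funding or recruitment, the section should name them.

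The cost is a short amendment and, if a stop occurs, up to 3 months of already planned follow-up for the children then in progress, using procedures that already exist.

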9. TRIAL PROCEDURES

9.1. Eligibility assessment

The eligibility of children to take part in CEDAR must be assessed by (a) a GCP-trained GP or other medically qualified doctor who has been trained in the trial procedures, OR (b) suitably qualified and GCP-trained Nurse or other healthcare professional, who has been trained in the trial procedures, and with oversight from a GCP-trained GP or other medically qualified doctor (or by an ANP with responsibility for the child's clinical care and under the conditions described in Section 6.11 above, 'Training and GCP requirements for recruiting sites').

Children's clinical data will be collected at baseline in line with the trial recruitment Standard Operating Procedure.

Prior to establishing whether the child is eligible to take part in CEDAR, verbal consent will be sought from the parent to conduct a detailed check of the eligibility criteria and this will be recorded on the CRF prior to recording whether the child meets the inclusion and exclusion criteria.

Informed consent should be obtained, and assent sought where appropriate, once the Recruiting Clinician has established that the child is eligible to take part.

9.2. Consent

The conduct of the trial will be in accordance with the Principles of Good Clinical Practice and applicable regulatory requirements. As all CEDAR subjects will be under 16 years of age, the legal parent or guardian's written informed consent is required for their child to participate in the trial. Sites will use the current, ethically approved version of the consent/assent forms, parent information sheet and other trial documentation.

Consent will be obtained for all children by (a) a GCP-trained GP or Nurse who has been trained in the trial procedures, OR (b) a suitably qualified other healthcare professional (GP or Nurse) who has been trained in the trial procedures by a GCP-trained GP, and with oversight from a GCP-trained GP (oversight in this instance is: (1) written confirmation from a GCP-trained GP that the member of staff is sufficiently qualified and experienced to take consent, on behalf of the recruiting site, for this trial; and (2) countersignature on the consent form by the GCP-trained GP prior to the issue of the trial medication).

Informed consent

Children under 16 cannot consent solely on their own behalf for an IMP study.

As routinely happens in similar paediatric clinical intervention trials, consent will be taken by a medical or a nursing registered practitioner, who will:

- (i) Be competent to gain consent from parents on behalf of their children and to gain assent as appropriate from children who are competent to understand what is being asked within the study, and;
- (ii) Have undertaken GCP training within 5 years (or as required by the CCG or Local Health Board), and received study-specific training prior to the start of recruitment.

It is the responsibility of the Recruiting Clinician (or other healthcare professional if local practice allows and this responsibility has been delegated by the site PI as captured on the Site Signature and Delegation Log) to obtain written informed consent for each child prior to performing any trial related procedure.

Because CEDAR requires children to be recruited opportunistically, parents may not have time to read the complete Parent Information Sheet (PIS) within the recruitment consultation. Clinicians taking consent must ensure that they adequately explain the aim, trial treatment, anticipated benefits and potential hazards of taking part in the trial to the parent, and be satisfied that the parent has a full and sufficient understanding of what is

involved before being asked to give consent. The consenting clinician should also stress that the parent or child is completely free to refuse to take part or withdraw from the trial or from any specific aspect of the trial (if not full withdrawal) at any time. The parent (and child if this is appropriate) must be given an opportunity to ask questions which should be answered to their satisfaction. The right of the parent or child to refuse to participate in the trial without giving a reason must be respected. If the child appears distressed about taking part to a degree that the clinician finds concerning, parental informed consent must be considered invalid.

If the parent is interested in taking part but requires more time to read the PIS and consider participation, the clinician may ask them to sit in the waiting room while they see the next patient, and then call the parent and child back in. The PIS will contain the names and contact details for the study team so that the parent may contact them with any queries about the research, at any time.

If the parent expresses an interest in their child participating in the trial they should be asked to sign and date the current ethically approved version of the Informed Consent Form. Children who are able to understand what is asked of them within the study may be given a copy of the Child Information Sheet and sign an assent form if age appropriate.

The consenting clinician must then sign and date the form. A copy of the Informed Consent/Assent Form should be given to the parent/child, a copy should be scanned into the child's primary care medical notes, a copy filed and the original sent to the trial centre for filing in the Investigator Site File (ISF). Once the child is entered into the trial the subject's trial number should be entered on the Informed Consent/Assent Form maintained in the ISF.

Details of the informed consent discussions should be recorded in the subject's medical notes. This should include date of, and information regarding, the initial discussion, the date consent was given, with the name of the trial and a copy of the Consent Form (which will include the version number of the Parent Information Sheet). Throughout the trial the parent should have the opportunity to ask questions about the trial and any new information that may be relevant to the subject's continued participation should be shared with them in a timely manner.

Details of all parents approached about the trial on behalf of their children should be recorded on the Subject Screening/Enrolment Log. For children recruited at CED, OOH and WIC sites, with the parent's prior consent their General Practitioner (GP) should be informed that they are taking part in the trial. A GP Letter is provided for this purpose.

Assent

In CEDAR, children of school age (\geq 5 years) are expected to complete daily pain scores within the Symptom and Recovery Questionnaire (using the FPS-R) and all children recruited into the trial and who are allocated to one of the treatment arms will receive the ear drops. Where appropriate, the child's assent (indicating understanding of what they are participating in and their voluntary participation) should be sought, supported by the separate study Assent Form and Child Information Sheet (designed for children aged 6-10 years).

At the discretion of the clinician and parent, assent should be sought as appropriate given the child's competence, for children who are able to understand what is asked of them within the study (usually around 5 to 6 years of age but may be younger or older depending on cognitive development). Assent must be obtained before randomisation and after an age-appropriate explanation has been given of the treatment options and the manner of treatment allocation.

Proceeding without assent risks contravening the legal requirement for this to not be against the best interests of the child (in other words, the child's dissent would negate the adult consent in a trial such as this where involvement should be truly voluntary at the point of inclusion). Article 28 of the Declaration of Helsinki (http://www.wma.net/en/30publications/10policies/b3/17c.pdf) states that:

When a potential research subject who is deemed incapable of giving informed consent is able to give assent to decisions about participation in research, the physician must seek that assent in addition to the consent of the legally authorised representative. The potential subject's dissent should be respected.

Assent processes and expectations regarding the child's potential understanding of the risks and benefits of taking part, must also be proportionate given the requirement to recruit opportunistically within a routine consultation, and will be at the discretion of the Responsible Clinician and of the parent.

